14.0 STATISTICAL CONSIDERATION	
15.0 PUBLICATION PLAN	
16.0 REFERENCES	

1.0 INTRODUCTION

Introductory Statement

Since abnormal brain bioenergetic function may contribute to neurodysfunction and neurodegeneration in Alzheimer's disease (AD), manipulating brain bioenergetics may affect the symptoms or alter the course of this disease. Oxaloacetate (OAA) could offer a potential approach for manipulating brain bioenergetics. There is evidence that OAA, a Krebs cycle and gluconeogenesis intermediate, enhances glycolysis flux, supports oxidative phosphorylation, and favorably modifies bioenergetics-related infrastructures. Our pre-clinical studies have also shown that OAA activates the brain's insulin signaling pathway, reduces neuroinflammation, and activates hippocampal neurogenesis [1]. Based on these preclinical findings, a phase I pharmacokinetic (PK) study in six human AD subjects (the Pharmacokinetics of Oxaloacetate Study, or POX Study; NCT02063308) was performed. The POX Study found AD subjects tolerate 100 mg BID of OAA when administered over a one month period. No adverse events were reported.

The next logical step is to conduct a combination safety and target engagement (phase Ib) study to define an OAA dose that is safe and which engages brain bioenergetic metabolism. This study, the "Trial of OAA in AD" (TOAD) trial, is designed to accomplish these goals. The TOAD trial's primary endpoint is safety, with OAA doses that have not previously been studied in human AD subjects. One of the secondary endpoints is target engagement of brain bioenergetics by OAA. The TOAD trial will use magnetic resonance spectroscopy (MRS) and fluorodeoxyglucose positron emission tomography (FDG PET) to assess brain bioenergetic target engagement. Exploratory target engagement data generated during this study will inform future study design. Another secondary endpoint is establishment of a pharmacokinetic profile of OAA at doses that have not been previously tested.

It is hypothesized that OAA, when orally ingested in adequate amounts, is safe and will alter brain bioenergetics. We further hypothesize that the doubling of the OAA dose will result in a doubling of the plasma OAA concentrations and that plasma OAA levels will correlate with our brain bioenergetics engagement outcomes (FDG PET and MRS). The following objectives are proposed to test these hypotheses.

2.0 OBJECTIVES

Primary Objective

The primary objective of the TOAD trial is to determine the safety and tolerability of OAA at doses up to 2 g/day. A dose escalation strategy will be used, which will involve first testing a 1 g/day OAA dose (500 mg po BID) taken for 4 weeks in 15 AD subjects. If this dose proves to be safe, 2 g/day OAA (1000 mg po BID), taken for 4 weeks in 15 subjects, will be tested. As part of the safety analysis, the following measures will be obtained: pre and post-treatment vital signs, safety labs, physical and neurological examinations, and cognitive testing data. We predict both OAA treatment doses will prove to be safe and well-tolerated.

Secondary Objectives

One of the secondary, exploratory objectives will be to test whether OAA (administered at 500 mg BID or as 1000 mg BID) has an observable effect on brain bioenergetics. Enhancement of brain glucose utilization on FDG PET, and changes in brain metabolism intermediates on

MRS, will be evaluated in both the 1 g/day dose and the 2 g/day dose cohorts. FDG PET and MRS will be measured at pre-treatment (just prior to starting OAA), and at post-treatment (just prior to stopping OAA, after approximately one month of treatment). The pre and post-treatment scans will be quantitatively analyzed and compared. We predict a dose will be found at which the post-treatment FDG PET scans show increased cortical glucose utilization, and that a dose will be found at which the post-treatment MRS scans show increased lactate and possibly other metabolite changes.

Another secondary objective is to define OAA PK properties. Specifically, we will determine plasma OAA levels after 500 mg and 1000 mg doses, to determine if a maximum absorption capacity is reached with these doses. We will also test for correlations between plasma OAA levels and brain bioenergetic biomarker, as revealed by FDG PET and MRS.

3.0 BACKGROUND

Prevalence

The elderly constitute a rapidly growing demographic. This reflects public health initiatives and medical advances that reduce risks and provide treatments for many previously terminal disorders. An increasing population of neurodegenerative disease victims is arguably the biggest downside to this success. For several common neurodegenerative diseases incidence rises with advancing age and prevalence is quite high [2]. Alzheimer's disease (AD), the most common neurodegenerative disease, affects 5.4 million Americans and one in every eight Americans over 65 is estimated to have it [3]. Society is also affected, as families and friends of AD patients provide most day-to-day care and altogether AD now costs our economy \$385 billion annually [4].

Rationale for Use

Mitochondrial dysfunction occurs in AD and is felt by many to be disease-relevant and a promising therapeutic target [5]. In AD brains various mitochondria-localized enzymes show reduced activity, and in most neurons intact mitochondria are numerically reduced [5]. Glucose utilization, as demonstrated by FDG PET, is also reduced in the AD brain [6]. For these reasons we believe that for AD, increasing mitochondrial mass, mitochondrial respiration, and glucose utilization are all well-justified mitochondrial medicine approaches and we are currently exploring ways to accomplish these endpoints [7]. Our efforts are informed by caloric restriction, which promotes liver mitochondrial biogenesis in some but not all studies, and exercise, which promotes muscle mitochondrial biogenesis. While we and others find caloric restriction and exercise do affect the brain in specific ways, and may even induce some degree of brain mitochondrial biogenesis less robustly than they affect liver and muscle. We therefore feel approaches that directly and robustly enhance bioenergetic fluxes (glycolysis and respiration-related) and brain mitochondrial biogenesis pathways are needed, and predict such approaches will benefit persons with AD.

The ideal agent would be systemically safe, cross the blood brain barrier, access neurons and astrocytes, activate mitochondrial biogenesis, increase respiratory capacity, and increase glycolysis capacity. OAA putatively meets these criteria (see preliminary data in section 8.0 CORRELATIVE STUDIES).

Description of Study Agent

OAA is a Krebs cycle and gluconeogenesis intermediate. It forms a redox pair with malate and is reduced to malate in a reaction that consumes NADH and generates NAD+. This would predictably shift cell redox balances towards more oxidized states, an effect reported to initiate mitochondrial biogenesis and mediate at least some health benefits of caloric restriction and exercise. OAA, following its reduction to malate, can also access mitochondria and thereby supply carbon to the Krebs cycle and respiratory chain. Finally, OAA is converted to phosphoenolpyruvate (PEP) by PEP carboxykinase (PEPCK), a reaction that comprises part of the gluconeogenesis and glyceroneogenesis pathways. Muscle PEPCK overexpression, possibly due to enhanced glyceroneogenesis, induces a profound muscle mitochondrial biogenesis, enhances respiratory fitness, and robustly extends lifespan [8]. Currently, OAA is commercially available and marketed as a nutritional supplement.

4.0 PARTICIPANT SELECTION

Subjects will be recruited through the University of Kansas Alzheimer's Disease Center's (KU ADC) Clinical Core Cohort/ Registry program. As part of their participation in the KU ADC Clinical Core Cohort/Registry, individuals receive clinical dementia rating (CDR) and Uniform Data Set (UDS) evaluations. Participant diagnoses, which are primarily based on CDR and UDS data, are determined through a consensus conference that includes subspecialty-trained cognitive neurologists and an expert neuropsychologist. Participants diagnosed with AD further meet current McKhann el al. criteria for that diagnosis [9].

The TOAD trial will enroll participants with mild AD as determined at the last KU ADC Clinical Core/ Registry evaluation. Each participant must have a study partner. The study partner will be someone who knows the participant well (typically a spouse, relative, or friend of the participant) and is able to answer questions about the participant's changes in health and/or behaviors over the course of the study. In addition, the study partner will administer the study medication and agree to accompany the participant to all study visits.

Enrollment Information

The TOAD trial will enroll a total of up to 36 participants, to ensure 15 participants in each dose cohort, 1 g/day and 2 g/day, complete the full intervention. No participant will be enrolled into the 2 g/day cohort until all 15 participants have completed the 1 g per day dose and it is established that the maximum acceptable dose-limiting toxicity (DLT) event rate has not been exceeded and it is safe to test the higher dose (See Safety section). Participants who complete the 1 g/day dose study may be invited to participate in the 2 g/day dose study, if still eligible and the principal investigator deems safe to do so.

Inclusion Criteria

Individuals are eligible if they meet the following criteria:

- 1. Age 50-85;
- 2. Have a diagnosis of probable AD per McKhann et al. criteria [9];

- 3. Have a clinical dementia rating (CDR) score of 0.5 or 1 AD at time of their last KU ADC assessment;
- 4. Have a Mini Mental Status Exam (MMSE) score of 15-28 *at the TOAD screening visit*;
- 5. Have a reliable and competent study partner who is willing to accompany the participant to all study visits, monitor compliance of study medication administration, and observe/report any changes in the participant's health throughout the study duration;
- 6. Are on stable doses of concurrent medications for at least 4 weeks prior *to the TOAD screening visit*; and
- 7. Speaks English as his/her primary language.
- 8. If female of child-bearing potential, must have a negative urine pregnancy test *at TOAD screening visit* (and must agree to use of contraception throughout the trial)

Exclusion Criteria

Individuals are ineligible if they meet any of the following criteria:

- 1. Dementia due to causes other than AD;
- 2. Potentially confounding, serious, or unstable medical conditions such as:
 - insulin-dependent diabetes mellitus
 - cancer within the past 3 years (except basal cell, squamous cell, or localized prostate cancer)
 - a recent cardiac event (i.e. heart attack, angioplasty, etc. within the 6 months prior to screening visit)
 - other conditions that pose a potential safety risk or confounding factor in the investigator's opinion;
- 3. Any abnormal physical examination assessment or vital sign assessment *at TOAD screening visit* that is deemed to be clinically significant by the principal investigator;
- 4. Any abnormal clinical laboratory test result *at TOAD screening visit* that is deemed to be clinically significant by the principal investigator.
- 5. Any contraindication for undergoing MRS, such as the presence of metal implants, a cardiac pacemaker that is not compatible with MRS, or severe claustrophobia

5.0 TREATMENT PLAN

Study Design

The TOAD protocol is designed as a phase Ib study that will provide information needed to plan a phase II study, or else indicate additional development work that is required before pursuing a phase II study. A dose escalation strategy will be utilized to contribute knowledge to the safety profile of OAA and to establish an effective target engagement dose. The primary outcome measure is the safety of currently untested OAA doses (1 g and 2 g per day) in AD subjects, as defined by safety laboratory tests, vital signs, physical and neurological examinations, cognitive changes, and reports of adverse events. Our secondary exploratory measures will determine a) whether these OAA doses have an observable effect on brain glucose utilization, as determined by FDG PET, and on levels of metabolism-relevant neurochemicals, as demonstrated by MRS and b) the PK properties of OAA at 500 mg and 1000 mg doses and whether OAA plasma levels at these doses correlate with FDG PET and MRS biomarker data.

Safety Outcomes

1 g/day and 2 g/day doses were selected for the following reasons. The POX Study has already indicated 100 mg BID is well-tolerated in AD subjects. Higher doses have not been specifically tested in AD subjects, but in a 1968 OAA clinical study (in diabetics) OAA dosed to 1 g/day for up to 44 days was found to be safe [10]. Also, we are aware that humans with glioblastoma have tolerated 2-3 grams per day for extended periods (in 2012, OAA was given "orphan drug status" for the treatment of gliomas). Ranging our study between 200 mg/day and 2 g/day, therefore, seems justified, especially since we are using a dose escalation approach in which safety at the 1 g/day dose determines whether we attempt the 2 g/day dose.

The maximum number of subjects in an arm who at any time are at risk of experiencing a dose limiting toxicity event will be capped at 3; at no time will the number of subjects that can potentially experience a dose limiting toxicity event in an arm exceed 3. This limitation will be achieved through curtailment. If any 2 among the first 6 subjects experiences a dose limiting toxicity we will discontinue that arm at that time. For a given arm, therefore, the risk to our subjects will be no greater than the risk of a traditional 3+3 design. The occurrence of a dose limiting toxicity event in 3 subjects in an arm terminates that arm, or 2 dose limiting toxicity event will put a hold on further enrollment pending review by our Data Safety Monitoring Committee, while the appearance of any serious adverse event will require placing the entire study on hold pending review by the Data Safety Monitoring Committee, our Institutional Review Board, the FDA, and the PI. In order to advance to the higher dose arm, only up to 1 of the first 6 subjects (16.7%) or up to 2 of the planned 15 subjects (13.4%) can experience a dose limiting toxicity; the occurrence of dose limited toxicity events in 2 of the first 6 subjects or 3 of the planned 15 subjects terminates the arm.

No participants will be enrolled into the 2 g/day dose cohort until the 1 g/day cohort is completed within the acceptable DLT range. If the 1 g/day dose is discontinued due to an unacceptable rate of DLT events, instead of testing a higher dose we will instead test a lower dose (500 mg/day, given as 250 mg BID). If the 1 g/day cohort is found to be safe but the 2 g/day cohort is not, remaining subjects will be switched to (if already in the study) or placed on (if not already in the study) 750 mg/day (375 mg BID).

Biomarker Outcomes

The TOAD study will utilize FDG PET and MRS as target engagement biomarkers. FDG PET and MRS data interpretation, however, is complicated by the fact that different interpretation strategies can be utilized and obviously with MRS there are multiple potential outcome measures. For these reasons, FDG PET and MRS data will be treated as secondary outcomes. Changes in these outcomes will nevertheless greatly inform the design of future OAA clinical trials.

In our preclinical mouse MRS studies, pre and post-treatment scans performed on 8 mice were sufficient to show treatment-associated lactate differences [1]. Increased lactate levels in the brains of mice receiving daily 2 g/kg intraperitoneal (IP) OAA injections could potentially reflect an OAA-mediated increase in glucose utilization. If so, FDG PET may provide a reasonably sensitive way to detect increased glucose utilization. Further, considering MRS and FDG PET data together could provide novel insight into bioenergetic fluxes present within the brains of AD subjects.

Fifteen participants per cohort is a reasonable enrollment goal to examine this secondary objective. In our preliminary mouse MRS studies, pre and post-treatment scans performed on 8 mice were sufficient to show treatment-associated lactate differences. This is not to imply 15 subjects per group is "conservatively powered", since there is at best a very limited ability to extrapolate data from mice receiving 2 g/kg IP OAA and scanned by a 9.4T magnet to humans receiving 500 or 1000 mg po BID and scanned by a 3T magnet.

More applicable are FDG PET data previously reported by Keller et al. [11]. That study was able to demonstrate an increase in the FDG PET-determined cerebral metabolic rate of glucose (CMRglu) in 13 AD subjects placed on galantamine and subsequently maintained on the drug for

12 months. If OAA at the doses in the current TOAD study is able to influence glucose utilization as robustly as galantamine, an n=15 per group should provide a reasonable chance of detecting a treatment-induced change if one exists, while providing a small cushion in the event of subject-drop out or if, as is possible, occasional individual scans prove to be of limited quality. Moreover, the short study duration (4 weeks) will ideally minimize drop-outs. In this respect, to our knowledge this will be the first study to compare pre and post-treatment PET FDG data at a 4 week time point. This is justified given our preliminary data, which indicate OAA rapidly affects brain bioenergetics [1].

Assuming safety outcomes are met for a particular cohort, lack of change on both the MRS and FDG PET target engagement biomarkers would argue that rather than progressing to a more advanced clinical trial phase, we will need to acquire additional very-early stage test data, such as the PK of 500 mg and 1000 mg doses to see if there is a linear relationship, and ideally to test the safety of higher OAA doses. If there is a more robust degree of target engagement with 2 g/day than the 1 g/day dose, further studies will examine safety and target engagement biomarkers at doses above 2 g/day to see if the higher doses provide more robust target engagement. If equivalent target engagement biomarker changes are seen at 1 g/day and 2 g/day OAA, the 2 g/day dose will move forward in subsequent studies. Ultimately, future studies will utilize the data from the TOAD study to define a specific target engagement biomarker analysis. Specifically, if positive MRS data emerge, results from this study will inform which metabolites are informative. Positive FDG PET data will tell us which brain regions are most informative.

Pharmacokinetics (PK)

We recently conducted an OAA PK-Safety study in AD subjects (see section 8.0 Correlative Studies / Clinical Studies). To measure PK in this study, plasma was prepared and analyzed for OAA concentration using a commercially-available coupled enzyme assay kit. Our data indicate that following oral administration the Tmax for OAA occurs between 1 and 1.5 hours.

We have recently developed a liquid chromatography-tandem mass spectroscopy (LC-MS/MS) based assay for OAA quantification that will provide sensitivity greater than what can be obtained through the coupled enzyme method. For the TOAD-PK analyses, we will use the LC-MS/MS-based assay to quantify OAA across a broader range of plasma concentrations.

Study Procedures

At the initial screening visit (V1), participants will undergo the following procedures: informed consent, medical history and symptom inventory, review of concurrent medications, Mini Mental Status Examination (MMSE), fasting safety labs (to include complete blood count, serum electrolytes, serum liver function tests, glucose) vital signs, and a physical and neurological examination. If the participant is a female of childbearing potential, a urine pregnancy test must be conducted. Once eligibility for the study is confirmed and within 14 days of this, participants will complete the baseline visit (V2). The baseline visit will include FDG PET, MRS, and the safety cognitive battery which consists of the ADAS Cog, Logical Memory I and II, and the Stroop Color Word Test. After all other baseline procedures are completed, study medication will be dispensed.

Participants (and their study partners) will be instructed to take the study medication two times a day in both the 1 g/day and the 2 g/day cohorts. In the 1 g/day dose cohort, participants will take 500 mg OAA BID for 4 weeks. The 2 g/day cohort will take 1000 mg OAA BID for 4

weeks. Participants will take their first dose of study medication in the clinic in each cohort and blood samples will be drawn just prior to administration of study medication, at 60 minutes post ingestion, and at 90 minutes post ingestion.

At the end of weeks 1, 2, and 3 of OAA administration we will place a phone call to enrolled subjects and their caregivers to ascertain side effects that could indicate emerging toxicity. Approximately 4 weeks (+/- 7 days) after starting study medication, participants will be asked to complete V3, which will include a post-treatment FDG PET, MRS, a repeat cognitive battery (including MMSE), review of symptoms (to check for adverse events), review of concurrent medications, fasting safety labs, vital signs, and physical/neurological examination. All used and unused study medication will be returned and study medication compliance will be calculated. The V3 FDG PET and MRS will be conducted while still taking study medication but just prior (within 7 days) to stopping.

A final phone interview (V4) will be conducted approximately 4 weeks (+/- 7 days) after stopping study medication to review the symptom inventory and determine if any adverse events were experienced in this time period.

Description of FDG PET Procedures

FDG PET images will be obtained at a satellite location of the University of Kansas Hospital. The scanner is accredited by the American College of Radiology (ACR), and our physicists perform annual required testing by scanning an Esser PET phantom with 18F to assess SUV range, contrast resolution, spatial resolution, and uniformity. In addition to the ACR annual testing, the nuclear medicine department routinely performs quality control procedures on a daily, weekly, and quarterly basis. Subjects will arrive for FDG PET after having fasted for a minimum of 6 hours and will have a catheter placed for IV administration of FDG. Subjects will receive a single IV bolus of FDG. After the appropriate amount of time has elapsed, frames are reconstructed to a single PET image in native space. Adverse events will be continuously monitored during the imaging session. The radiation dose from the two FDG PET scans our subjects will receive will not exceed 2100 mrem. While this amount of radioactivity obviously exceeds the amount obtained through normal background exposure, it is still considered by Radiation Safety to be well below the risk levels acceptable in research and medical practice.

Description of MRS Procedures

MRS scans will be obtained using a 3T system (Skyra, Siemens, Erlangen, Germany) fitted with a 12-channel receiver head coil. After positioning the participant supine in the magnet, three-plane scout MR images are acquired followed by an oblique-axial MP-RAGE sequence oriented parallel to the AC-PC line. We will collect several MRS sequences to sample a large spectroscopic imaging slab at the same angle, superior to the lateral ventricles. From this we will determine concentrations of several neurochemicals including lactate, glutamine, and glutamate which are of specific relevance to the current proposal. We will also quantify glutathione from the same locations using a double-quantum filtered sequence developed at the Hoglund Brain Imaging Center. In addition, based on our animal results we will also acquire a single voxel spectrum that includes the hippocampus. Scan time will be approximately 1.5 hours, which from our experience is feasible in this subject group. Spectra will be analyzed using LCModel and corrected for tissue fraction in each voxel using the segmented MP-RAGE images corresponding to the spectroscopic imaging slab, and using existing laboratory routines.

Description of Pharmacokinetic Procedures

In each cohort (500 mg OAA bid and 1000 mg OAA bid), the participant will consume the first dose of study medication in the clinic, after having fasted for a minimum of 8 hours. Just prior to administration of this first dose, a blood PK sample (approximately 4 mL of blood) will be drawn to provide a baseline measurement. A second PK sample will be drawn at 60 minutes post ingestion and a third PK sample will be drawn at 90 minutes post ingestion. Each PK sample will immediately be placed on ice, and will be processed into plasma within 10 minutes of collection. Aliquots of plasma (approximately 0.5 mL each) will be frozen and stored at -80°C immediately until analyses. Quantitation of OAA in plasma will be performed using the LC-MC/MS based assay described above.

Procedure Timeline

The timing of study procedures/schedule of events are summarized in the STUDY CALENDAR in Section 9.0

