OAA treatment enhanced the brain insulin signaling pathway activation state. Akt Ser473, mTOR Ser2448, and P70S6K Thr389 phosphorylation increased. OAA treatment also reduced markers of neuroinflammation. Hippocampal C-C motif chemokine 11 (CCL11) mRNA, hemisphere nuclear factor κ B (NF κ B) protein levels, and NF κ B nucleus-to-cytoplasm ratios were lower than in control mice.

It was previously reported in mice that CCL11 retards subgranular layer neurogenesis [17]. Because CCL11 gene expression was reduced in the hippocampus of OAA-treated mice, and because Akt and mTOR activation promotes cell growth, we evaluated hippocampal neurogenesis and found enhanced hippocampal neurogenesis. Hippocampal vascular endothelial growth factor A (VEGF) mRNA levels increased. Hippocampal mRNA and protein levels of doublecortin (DCX), which is commonly used as a surrogate measure of new neuron formation, increased. The number of intensely DCX-positive neurons increased. Relative to the control group, DCX-positive neurites were longer in the OAA-treated mice.

¹H-MRS was performed on mice before receiving any treatment, and on the same mice after they received 2 g/kg/day OAA IP for one week (the 1 g/kg/day dose was not studied). OAA induced changes in several neurochemicals. After one week of OAA, brain lactate, GABA, and glutathione (GSH) levels were respectively 21%, 15%, and 27% higher than they were on the pre-treatment scans.

Clinical Studies

Prior to our own recent OAA studies, the literature reported only one human study of OAA, a 1968 study that evaluated its potential anti-hyperglycemic effects. This study, performed in human diabetics, reported OAA was well-tolerated and also limited PK data [10]. Levels were not increased 30 minutes but were increased 60 minutes after 200 mg were orally administered to three subjects. On average, OAA levels rose from 0 ug/100 ml to 2.3 ug/100 ml.

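### Without an untreated or scan-rescan comparator, similar biomarker change at both doses cannot separate a drug effect at plateau from a first-to-second-scan difference, yet the protocol moves forward on it

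*Protocol*

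**What the plan says.** Section 2.0 (Secondary Objectives) defines the biomarker comparison within the person: "The pre and post-treatment scans will be quantitatively analyzed and compared". Section 5.0 (Study Procedures) and the Section 9.0 calendar place one FDG PET and one MRS before the first dose and one of each about four weeks later, still on drug.

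Both cohorts are treated. Section 4.0 plans enrolment "to ensure 15 participants in each dose cohort, 1 g/day and 2 g/day, complete the full intervention", and no placebo, untreated or test-retest group is described anywhere. The cohorts run one after the other: "No participant will be enrolled into the 2 g/day cohort until all 15 participants have completed the 1 g per day dose". They may also share people: "Participants who complete the 1 g/day dose study may be invited to participate in the 2 g/day dose study".

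Section 5.0 (Biomarker Outcomes) then sets out how the results will be used. No change on either modality argues against progressing. A stronger response at 2 g/day leads to work at higher doses. The third case is: "If equivalent target engagement biomarker changes are seen at 1 g/day and 2 g/day OAA, the 2 g/day dose will move forward". Correlations between plasma OAA and the imaging measures are planned in Sections 2.0 and 5.0, but they are not a condition of any of these branches.

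**The concern.** A pre/post difference in an uncontrolled cohort is the sum of any drug effect and anything else that differs between a first and a second scan: familiarity with the scanner, anxiety, the passage of time. A non-drug component of this kind does not depend on dose, so it would tend to appear at a similar size in both cohorts. That is the pattern the third branch treats as grounds for moving forward. None of the branches allows for a change that OAA did not cause.

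The supporting evidence in the protocol does not fill the gap. The mouse spectroscopy has the same before/after structure: "MRS was performed on mice before receiving any treatment, and on the same mice after they received 2 g/kg/day OAA IP for one week". Control mice are mentioned in Section 8.0 for other measures, but not for MRS. For FDG PET the protocol notes that "to our knowledge this will be the first study to compare pre and post-treatment PET FDG data at a 4 week time point", and it gives no scan-rescan figure for that interval.

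At stake is whether later studies start from an engagement claim that this design could not establish. Enlarging the cohorts would not help, because a systematic shift is detected more reliably as n grows.

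**Working it through.** **Is there a stated figure to reproduce?** No. Section 5.0 says only that "an n=15 per group should provide a reasonable chance of detecting a treatment-induced change if one exists". It gives no alpha, SD, effect size or power for the biomarkers. The argument is therefore about design logic, and the arithmetic only illustrates it.

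**The logic.** Write the mean pre/post change in cohort k as s_k + e_k, where s_k is the scan-order or time component and e_k the drug effect.
- Plateau: e_1 = e_2 = e > 0 and s_1 = s_2 = 0. Both cohorts change by e.
- Inert drug with a common shift: e_1 = e_2 = 0 and s_1 = s_2 = s. Both cohorts change by s.

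With no group in which e is known to be zero, these two cases predict the same pre/post means.

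**How often an inert drug would reach the branch.**

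From the protocol: n = 15 per cohort.

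Assumed:
- one outcome, with independent normal changes in the two cohorts;
- a shared upward shift d, in SDs of the within-person change;
- change is seen if a paired t-test at two-sided 5% is significant upward;
- equivalent means a non-significant two-sample t-test between cohorts.

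For one cohort, the probability of a significant rise is P1 = P(T > 2.145), where T is noncentral t with 14 degrees of freedom and noncentrality d × √15. For both cohorts it is P1². The last column adds the requirement of no significant cohort difference and comes from simulation.

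| Shift d | d × √15 | P1 | P1² | Both rise, no significant difference |
|---|---|---|---|---|
| 0 | 0 | 0.025 | 0.0006 | about 0.1% (0.06%) |
| 0.3 SD | 1.16 | 0.190 | 0.036 | about 4% |
| 0.5 SD | 1.94 | 0.438 | 0.192 | about 19% |
| 0.8 SD | 3.10 | 0.821 | 0.675 | about 66% |

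The last two columns are close because, once both cohorts have risen, at least 96% of simulated trials show no significant dose difference at any shift up to 1.0 SD. An inert drug that gets this far almost always lands in the equivalent-change branch.

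**What a comparator would do.** Under the same assumptions, add an untreated group of 15 scanned twice and test each dose against it. The chance that both doses exceed it with no dose difference is then about 0.4–0.5% at every shift from 0 to 1.0 SD.

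**What the planned plasma correlation can add.** Blood is drawn only before, 60 minutes after and 90 minutes after the first dose (Section 5.0), about four weeks before the second scan. By the Fisher z approximation, 80% power at two-sided 5% with n = 15 needs z = (1.960 + 0.842)/√12 = 0.809, that is r = tanh(0.809) ≈ 0.67. Only a strong correlation would be found reliably.

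**The case against.** The best defence is that this is a phase Ib trial with safety as its primary endpoint. The biomarkers are labelled secondary and exploratory, their interpretive difficulty is admitted, and Section 5.0 disclaims conservative powering. The disputed sentence names changes in biomarkers and picks a dose for later work; it does not say in terms that engagement is proven. All of this is fair. It keeps the point to one of wording and does not make the missing control arm an error. It does not remove the problem, because the same section describes the trial as establishing a dose that engages the target, and the branch acts on the pattern with no condition on its cause.

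Three stronger readings are tempting and are not supported.

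- *Equal change shows that OAA did nothing.* It does not. Section 2.0 asks whether absorption reaches a maximum at these doses, and a real effect at plateau gives the same picture. The pattern leaves the cause undetermined.
- *Only a difference between doses could identify a drug effect.* The plasma correlation is already planned and is another source of evidence, though a weak one. A dose difference is itself open to doubt. The cohorts are sequential, so calendar time differs, and 1 g/day completers who re-enter will already have been scanned twice. For the same reasons a scan-order shift need not be identical in the two cohorts.
- *A false engagement claim is likely.* Nothing in the protocol shows that a second-scan shift exists, or gives its size or direction. With no shift the illustrated probability is about 0.1%, and a downward shift would not match the increases that Section 2.0 predicts.

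**Conclusion.** The point holds as one about inference. Similar FDG PET or MRS change at both doses, with no untreated or scan-rescan comparator, cannot distinguish a plateau drug effect from a dose-independent difference between first and second scan, and the protocol's branch proceeds as if it could. This part needs no numerical assumption.

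The size is illustrative only: from about 0.1% with no shift to 66% with a shared upward shift of 0.8 SD, for an inert drug and one outcome, with the tests and the meaning of equivalent supplied here. Where the trial would fall in that range cannot be determined from the protocol. The exploratory status of the biomarkers limits the consequence, but the remedy is cheap enough to be worth making.

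**What to change.** Reword the equivalent-change branch in Section 5.0 (Biomarker Outcomes) along these lines:

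- Similar change at both doses is reported as a pre/post change of undetermined cause and does not by itself count as target engagement.
- Attribution to OAA rests on supporting evidence. This is either the planned correlation of plasma OAA with the biomarkers, stating that sampling covers only the first dose and that power is low with 15 per cohort, or available untreated scan-rescan data for the same measure over a comparable interval.
- Where neither is available or convincing, the question is left to a concurrent control group in the next study.
- A difference between doses is supportive only, because the cohorts are sequential and 1 g/day completers may re-enter.

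The cost is that one favourable exploratory outcome becomes inconclusive. The rewording adds no participants or scans to this trial. Suitable untreated rescan data may not exist, in which case that route is closed and the result stays inconclusive. The change concerns what may be concluded about engagement and takes no position on which dose should advance.
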